## **7.4 Data Analysis and Reporting**

In general data analysis will be performed across all subjects, as well as within each of three groups (Group A, B and C), based on Primary Analysis population unless otherwise specified.

The data collected will be presented using the appropriate summary statistics. Continuous data will be summarized using descriptive statistics (mean, number of observations, standard deviation, minimum and/or maximum values) and categorical data will be summarized using frequencies and percentages.

### **7.4.1 Primary objective**

The mean reduction of office SBP at six (6) months of the study will be analyzed by:

1. Computing the reduction of SBP measurements at 6 months compared to baseline for each patient with data available in both time points.
2. Calculating the mean and standard deviation of the SBP reduction at 6 months

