The one month clinical results from EnligHTN I were presented at the European Association of Percutaneous Cardiovascular Interventions, EuroPCR 2012 Congress May 15-18, 2012. Data was presented on 46 patients from four sites (60±10 years, 15 females/ 31 males) with a baseline average office Blood Pressure (BP) measurement of 176±16 / 96±14 mmHg, and an average of 4±0.6 anti-hypertensive medications. Fifteen (15) patients had a history of Diabetes Mellitus Type II. Median procedure time was 34.0 with a mean number of ablations completed on the right side of 7.7±0.8 and the left side of 7.4±1.4. One patient had the renal denervation procedure completed on the right side only due to tortuous anatomy. No vascular or renal artery complications were observed at the end of the procedure in any of the patients. At the time of discharge the average Blood Pressure measurement was 154/88 mmHg and at the one month time point the average office Blood Pressure measurement was 148/87 mmHg. The average systolic / diastolic Blood Pressure between baseline and one month was -28/-10 mmHg with 78% of the patients experiencing a ≥ 10 mmHg reduction in systolic Blood Pressure.

The three month clinical results from EnligHTN I were presented at the European Society of Cardiology (ESC) meeting on 28 August 2012. At the three month time point the average systolic / diastolic Blood Pressure difference between baseline and three month follow-up was -27/-10 mmHg with 80% of the patients experiencing a ≥ 10 mmHg reduction in systolic Blood Pressure. At 3 months, the mean systolic/diastolic ambulatory Blood Pressure difference between baseline and 3 months was -9.9/-5.4 mmHg.

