## 3.2 Objectives

### Primary Objective

The primary objective is to evaluate a mean reduction in office Systolic Blood Pressure at six (6) months across all subjects post renal denervation and within sub-groups.

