##### **4.3.1 Blood and Urine Analysis**

Blood and urine samples will be collected and analyzed as listed below.

- Serum Creatinine
- Estimated GFR (eGFR)

---

SJM CONFIDENTIAL AND PROPRIETARY

© 2012 – St. Jude Medical Cardiovascular Division: All rights reserved. No portion of this work may be reproduced in whole or in part without the express written permission of St. Jude Medical Cardiovascular Division.

Clinical Investigational Plan: EnligHTN II

- Hemoglobin A1c
- Fasting glucose
- Fasting insulin
- Urine albumin-creatinine ratio
- Pregnancy test (only at baseline)

A true numeric value for the estimated GFR must be provided. If your local laboratory does not report the eGFR value beyond 60 mL/min/1.73 m^2 the center should use a sponsor-approved calculation tool to generate the value. The sponsor will provide an approved website(s) for this calculation to study centers.

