#### **4.3.4 Quality of Life Questionnaire**

EQ-5D 5L questionnaire will be completed at baseline.

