## 4.4 Subject Group Assignment

Subjects who have met all of the baseline and enrollment criteria will be assigned to one of the following groups:

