### 4.4.1 Group A: (minimum of 100 subjects)

- Office systolic Blood Pressure  $\geq 160$  mmHg
- Subject is taking  $\geq 3$  anti-hypertensive medications (including 1 diuretic), or subject has documented drug intolerance to 2 or more of the 4 major classes of anti-hypertensives (ACE/ARB, Calcium Channel Blockers, Beta Blockers, or diuretic) and is unable to take 3 anti-hypertensive drugs.
- Patient has an estimated GFR  $\geq 45$  mL/min per  $1.73 \text{ m}^2$  using the Modification of Diet in Renal Disease (MDRD) formula

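### Does leaving the baseline office SBP reading unnamed bias the primary within-group reductions through regression to the mean?

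*Combined protocol and SAP*

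**What the plan says.** The primary objective (Section 3.2) is the mean fall in office SBP "at six (6) months across all subjects post renal denervation and within sub-groups". Section 7.4.1 obtains it by "Computing the reduction of SBP measurements at 6 months compared to baseline", for patients with both values, and then takes the mean and SD. Section 7.4 reports results over all subjects "as well as within each of three groups (Group A, B and C". Section 7.2 states that there is no power analysis and no hypothesis test.

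Table 1 schedules office SBP before the procedure at the Enrollment/Baseline visit and again at the Confirmatory visit. Section 4.1.3 asks for a further set if medication changes, and Section 4.3 does so if the subject is re-evaluated. The 140 mmHg entry criterion (Section 3.6.1) is tied to the Confirmatory visit.

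Section 4.4 says: "Subjects who have met all of the baseline and enrollment criteria will be assigned to one of the following groups". The Group A and Group B entries give "Office systolic Blood Pressure" limits of 160 and 140 mmHg, without a visit. Their drug and eGFR criteria are identical. Group B has no upper SBP limit.

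**The concern.** Two things are unstated: which reading is the baseline in 7.4.1, and which reading assigns the group in 4.4. The word baseline is also used loosely. Section 4.2.1 treats the return visit as part of the baseline evaluation. Section 4.3.4 says "EQ-5D 5L questionnaire will be completed at baseline" and Section 4.3.1 lists "Pregnancy test (only at baseline", yet Table 1 places both only in the Confirmatory column. Section 7.4.2.2 measures eGFR change from baseline, and Table 1 schedules the only pre-procedure eGFR at the Confirmatory visit.

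If a single noisy reading both sorts patients at 160 mmHg and starts the change score, Group A's fall is overstated. Group B's is generally understated if B means 140-159. With raw pre/post means and no control arm, the analysis could not separate this from a device effect. Readers comparing the groups might see a larger benefit in more severe hypertension that is not there.

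**Working it through.** **What the text points to.**

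- *Baseline.* Section 4.1 is titled as the Enrollment/Baseline visit and contains the office BP instruction (4.1.3). Table 1 has a column of that name, separate from Confirmatory. Appendix A lists Baseline among the office BP visits and omits the Confirmatory visit. Section 4.3 speaks of baseline and the screening period as earlier steps. All this favours the enrolment reading.
- *Grouping.* Assignment needs eGFR, which Table 1 first schedules at the Confirmatory visit. Section 4.4 follows 4.3 and applies once the criteria are met, and the SBP entry criterion is itself a Confirmatory reading. This favours the Confirmatory reading.

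On this reading the two roles fall to different visits.

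**Size if one reading did both jobs.** The plan has no figure to reproduce, because it states no visit-to-visit SD, correlation or expected reduction.

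Inputs:
- SD 16, from the feasibility study in Section 2 ("baseline average office Blood Pressure (BP) measurement of 176±16 / 96±14 mmHg"), used here as the SD of a patient's usual SBP.
- Visit SD *s* = 8, 10 or 12 (assumed).
- Mean *m* from 145 to 176 (assumed; 176 is the only documented value, and entry here starts at 140).
- No treatment effect.

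A single reading X has variance 256 + s². The false fall in a group is

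(1 - rho) × (E[X | group] - m), with 1 - rho = s² / (256 + s²).

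Example with m = 160, s = 10: the SD of X is √356 = 18.87 and 1 - rho = 100/356 = 0.281.

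| Group | E[X given group] | False fall (mmHg) |
|---|---|---|
| A, 160 or more | 175.05 | 0.281 × 15.05 = 4.2 |
| B read as 140-159 | 150.90 | 0.281 × (-9.10) = -2.6 |
| All 140 or more | 165.02 | 0.281 × 5.02 = 1.4 |

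The A-B gap is 6.8, and A exceeds all subjects at 140 or more by 2.8.

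Over the whole grid:
- A falsely falls by 1.2 to 9.6.
- B as 140-159 runs from a rise of 8.6 to a fall of 1.7.
- The A-B gap is 4.1 to 11.3.
- A exceeds all subjects at 140 or more by 1.0 to 4.9.
- All subjects together falsely fall by 0.2 to 4.7.

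At the documented mean of 176, A's false fall is only 1.2 to 2.7 and the all-subject figure is 0.2 to 0.6. With a visit SD of 5, the A-B gap is 1.8 to 2.5.

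**Size if the visits have separate roles** (Confirmatory groups, enrolment is baseline; simulation on the same grid, B as 140-159):
- Only the Confirmatory reading selects at 140: gap -0.04 to 0.04.
- Both readings select at 140: gap -3.1 to -0.8.
- Only the Confirmatory reading selects, and the two visits' errors correlate at 0.3-0.5: 1.2 to 5.6 remains.

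**Is enrolment a better baseline overall?** If only the Confirmatory reading selects, yes: the all-subject artefact is about 0. If both select, it is the same from either visit (1.0 mmHg from each at m = 160, s = 10). The enrolment reading also precedes the 14-day period in which compliance is urged (4.2.1), and it may lie up to 90 days before the procedure (3.6). A fall from better adherence would then count as treatment effect. The documents give no size for that.

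**The case for a change.** The strongest opposing case is that the labels do not settle the matter. Section 7.4.2.2 measures eGFR change from baseline in the same terms as 7.4.1, and there baseline can only be the Confirmatory visit. An analyst who followed that precedent for SBP, and grouped on the same visit, would produce exactly the artefact described. Its direction is certain for any visit-to-visit correlation below 1. The plan names a visit for the entry criterion, so it could have done so here. Nor does the absence of an A-versus-B test protect each group's own mean, which is part of the primary objective.

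Much of this stands: the definition is missing, two programmers could differ, and a sizeable artefact is possible. It does not show that the plan as written produces the artefact. For office SBP specifically, Section 4.1.3, the Table 1 column and Appendix A outweigh usage attached to other measurements, and that usage is inconsistent anyway: NYHA class sits in Section 4.3 but in the Enrollment/Baseline column of Table 1. The larger range also needs an upper limit on Group B that 4.4.2 does not contain. The overlap of Groups A and B is a separate matter of group definition, although it affects the size here.

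**Conclusion.** The omission is real, but the harm depends on one reading doing both jobs, and that is not the likeliest reading of the plan. In that case the artefact would be about 1-5 mmHg for A against all subjects at 140 or more, or about 4-11 mmHg for A against B as 140-159, beside a cited six-month fall of about 25 mmHg (Section 2). These figures rest on an assumed visit SD of 8-12, an assumed mean of 145-176 and no treatment effect. On the likeliest reading the gap is about zero, or about -3 to -1 mmHg if both readings select, with independent visit errors. Correlated errors would leave some of it.

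Prescribing the enrolment baseline would mostly write down what the structure already implies. It would also present as a cure what is a trade-off between regression to the mean and pre-procedure adherence. Both readings are collected, the analysis is descriptive, and analysts can state the reading used and show the other in the ordinary course of reporting. The same applies to repeat sets after a medication change. This is a gap that analysts can fill sensibly, and no change to the plan follows.

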### **7.4.2 The Secondary objectives**

#### **7.4.2.1 Safety Acute data (30 days post procedure)**

- The peri-procedural events within 30 days post procedure will be summarized as percentage of patients defined as:

$$\frac{\text{Number of subjects with peri procedural events within 30 days post procedure}}{\text{Number of subjects at baseline for that population}} * 100$$

**7.4.2.2 Safety Midterm (6 months) and Long term (2 and 5 years) data**

- The new renal artery stenosis (>50%) and/or aneurysm at the site of ablation per Renal Artery Imaging (CT/MR) will be summarized at 6 months, 2 and 5 years as percentage of patients who have stenosis and/or aneurysm. Kaplan-meier analysis may be performed on the time to the first new renal artery stenosis and/or aneurysm at the site of ablation, as appropriate.
- Renal function change based on eGFR will be summarized by:
  1. Computing the change of the eGFR at 6 months, 2 years and 5 years compared to baseline for each patient with data available in both time points.
  2. Calculating the mean and standard deviation of the eGFR change at those interval

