##### Midterm (6 months):

- Assessment of renovascular safety as measured by new renal artery stenosis or aneurysm at the site of ablation
- Renal function change based on eGFR

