#### **4.8.9 Renal artery evaluation**

Renal artery evaluation will be completed at the 6M, 24M, and 60M follow-up visit. Duplex Ultrasound (U/S) is the recommended imagine modality, however this evaluation can be completed by either: computed axial tomography (CT scan), duplex ultrasonography, Doppler,

angiography, magnetic resonance (MR) angiography or non contrast magnetic resonance imaging.

If a renal artery evaluation is completed at any other time point this data will also be collected during the study.

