### **7.3 Analysis Population**

All patients who have signed a Patient Informed Consent (PIC) will be considered enrolled in the study. However, Primary Analysis population will include those patients that have signed a PIC, and had the EnligHTN™ Renal Denervation System enter his/her body. The sample size of 500 are those subjects in the Primary Analysis population.

---

SJM CONFIDENTIAL AND PROPRIETARY

As Treated population will include all subjects in whom renal denervation was performed in a minimum of one renal artery per kidney (according to the Instructions for Use).

It is anticipated that there may be subjects who have enrolled in the study but are not included in the Primary Analysis population or As Treated population, such as:

- Subjects who are enrolled but do not meet baseline inclusion or exclusion criteria before the procedure; these are considered the screen failure population.
- Procedurally excluded populations will include subjects who have enrolled in the study and start the procedure, but do not have the EnligHTN™ Renal Denervation System enter his/her body, due to their anatomy, circumstances related to the procedure, or physician judgment.

Subjects that withdraw from the investigation will not be replaced in any analysis population.

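### The stenosis/aneurysm rate is defined on CT/MR although follow-up recommends duplex, and no rule covers subjects without an evaluable scan; read literally, both understate the rate

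*Combined protocol and SAP*

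**What the plan says.** All references are to the combined protocol and SAP.

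- **Objective (Section 3.2, and the Synopsis).** At 6 months, and again at 2 and 5 years: "Assessment of renovascular safety as measured by new renal artery stenosis or aneurysm at the site of ablation". No imaging modality is named.
- **Analysis (Section 7.4.2.2).** "The new renal artery stenosis (>50%) and/or aneurysm at the site of ablation per Renal Artery Imaging (CT/MR) will be summarized" at 6 months, 2 years and 5 years, as a percentage of patients. No formula is given. A Kaplan-Meier analysis is optional and has no censoring rule.
- **Follow-up imaging (Section 4.8.9).** The evaluation falls at the 6, 24 and 60 month visits. "Duplex Ultrasound (U/S) is the recommended imagine modality"; CT, Doppler, angiography, MR angiography and non-contrast MRI are also permitted. On unscheduled scans: "If a renal artery evaluation is completed at any other time point this data will also be collected during the study". Table 1 lists the evaluation without a modality.
- **Escalation (Section 4.3.5).** An investigator may consider CT or the procedural angiogram when duplex is inconclusive or abnormal. This is optional and sits in the baseline section only.
- **Population (Sections 7.3 and 7.4).** Analyses are "based on Primary Analysis population unless otherwise specified". "The sample size of 500 are those subjects in the Primary Analysis population". "Subjects that withdraw from the investigation will not be replaced in any analysis population".
- **Neighbouring items.** The eGFR change in the same section is computed "for each patient with data available in both time points". The proportion with office SBP below 140 (Section 7.4.2.3) is divided by subjects with 6 month data. The 30-day event rate (Section 7.4.2.1) has its own stated denominator.

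**The concern.** The analysis section and the procedures section describe different evidence for the same endpoint at the same visits. Taken as written, the test that the plan recommends cannot produce a countable event, and neither can catheter angiography, which is also permitted.

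The denominator adds a second problem. Section 7.4 supplies a population but no rule for a member with no scan, an unreadable scan or duplex only. Dividing by the whole population silently treats all of these as free of stenosis and aneurysm. Missing scans are foreseeable: withdrawn subjects are not replaced, and the final visit requested from them in Section 4.9 lists office blood pressure and laboratory tests but no renal imaging.

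At stake is the renovascular safety result at 6 months, 2 years and 5 years. The study is descriptive, so this percentage is itself the reported finding.

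**Working it through.** The plan states no expected rate, confidence level or precision target for this endpoint, so there is no figure to reproduce. The check is a comparison of texts, followed by an illustration.

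**Text comparison**

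| Question | Section 7.4.2.2 | Section 4.8.9 |
|---|---|---|
| Time points | 6 months, 2 and 5 years | 6, 24 and 60 months |
| Modality | CT/MR | Duplex recommended; CT, MR, Doppler, angiography permitted |
| CT/MR required? | Implied by the event definition | No, whatever duplex shows |
| Subjects without a scan | Not addressed | Not addressed |

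**Inputs.** N = 500 is from Section 7.3. Everything else is assumed: T = 10 true events (10/500 = 2.0%); f = share of subjects with CT/MR; s = share scanned by any modality; duplex detects every true lesion.

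**A. Only CT/MR counts; CT/MR is unselected and not prompted by duplex.** Rate shown over 500 = T × f / 500.
- f = 10%: 1/500 = 0.2%
- f = 30%: 3/500 = 0.6%
- f = 50%: 5/500 = 1.0%

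Dividing by CT/MR subjects instead gives 1/50, 3/150 and 5/250, each 2.0%. The exact (Clopper-Pearson) 95% intervals are then 0.05% to 10.65%, 0.41% to 5.73% and 0.65% to 4.61%, against 0.96% to 3.65% for 10/500.

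**B. Any modality counts, but only a share s is scanned, unrelated to event status.**
- s = 90%: 9/500 = 1.8%, against 9/450 = 2.0% among those scanned
- s = 80%: 8/500 = 1.6%, against 8/400 = 2.0%
- s = 70%: 7/500 = 1.4%, against 7/350 = 2.0%

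**C. A repair to avoid.** Suppose a cumulative 5 year figure is formed by adding subjects with an earlier event to those scanned at 5 years. Let all 10 events be found at 6 months and none later. The denominator is 500s + 10(1 − s).
- s = 90%: 10/451 = 2.2%
- s = 80%: 10/402 = 2.5%
- s = 70%: 10/353 = 2.8%

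The true value is 2.0%. Earlier events are all kept while event-free subjects who miss the later scan are dropped, so the figure is biased upward.

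**D. Cost of counting any modality.** Let sp be the assumed duplex specificity, with no CT/MR after duplex. The any-modality line over 500, with everyone scanned, is [10 + 490(1 − f)(1 − sp)] / 500.
- sp = 95%, f = 10%, 30%, 50%: 32.05, 27.15 and 22.25 over 500 = 6.4%, 5.4% and 4.5%
- sp = 90%, same f: 54.1, 44.3 and 34.5 over 500 = 10.8%, 8.9% and 6.9%

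An any-modality figure therefore cannot stand alone.

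**The case against.** The strongest reply is that the bracketed CT/MR is shorthand or an example. The objectives name no modality, CT and MR are permitted at follow-up, and a sensible analyst would count any confirmed lesion. That reading is possible, and the objectives favour it. The text does not state it, however, and a list of examples that leaves out the recommended test still needs correcting.

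A second reply is that other parts of the plan catch these events. Section 5.7.8 requires reporting of serious events and device effects, and the Clinical Event Committee adjudicates them (Section 12.3.2). Section 7.4 asks for frequencies as well as percentages, so counts will be visible. This stands in part: some lesions will surface there. But adjudication is not an imaging confirmation step, and it sets neither the numerator nor the denominator of this percentage.

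Third, the study is descriptive with no hypothesis test (Section 7.2), and every rate in the illustration is assumed. Both points are right. They limit the weight of the point but do not remove the inconsistency.

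A reader might also infer more than the documents support:
- **That there is no denominator at all.** Section 7.4 gives a default population. What is missing is the handling of members without an evaluable scan.
- **That the rate could be greatly overstated**, because CT/MR would be concentrated in subjects with a positive duplex and used as the denominator. The plan has no follow-up confirmation step and no CT/MR-only denominator.
- **That the 5 year figure might count only lesions found since the previous visit.** Nothing in Section 7.4.2.2 suggests this; a persisting lesion is still present at the later scan.

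**Conclusion.** The point holds as a conflict between Sections 4.8.9 and 7.4.2.2, joined to a missing rule for subjects without an evaluable scan. Followed literally over the default population, the rule understates the stenosis/aneurysm rate in two ways: lesions seen only on duplex, Doppler or angiography are left out, and unscanned subjects count as event-free.

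On the assumed inputs, a true 2.0% would read 0.2% to 1.0% through the modality restriction, or 1.4% to 1.8% through missing scans alone. These ranges rest on unselected CT/MR, on scanning unrelated to event status and on perfect duplex sensitivity, none of which the documents establish. The direction follows from the text; the size does not.

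This should be fixed before the imaging data are summarized. It concerns a secondary safety objective at three time points.

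**What to change.** Reconcile Sections 4.8.9 and 7.4.2.2 in the analysis text:

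1. **Event.** Count a stenosis above 50% or an aneurysm in the ablated segment on any modality that Section 4.8.9 permits, scheduled or unscheduled. Report by modality, with separate lines for CT/MR confirmed, CT/MR negative and no CT/MR done.
2. **Percentage.** Make the 6 month, 2 year and 5 year figures visit-specific. The denominator is subjects with an evaluable scan at that visit, and the number not imaged is shown beside it. A lesion found only on an unscheduled scan is listed with its date and enters item 3; it is not added to a visit's numerator unless the subject is in that visit's denominator.
3. **Cumulative figure, if wanted.** Take it from a time-to-event estimate that censors event-free subjects at their last evaluable scan and recognises that onset is known only to lie between two scans. Do not add earlier events to a visit-specific denominator.

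**Cost.** Analysis wording and a few table lines, with no extra imaging and no change to the clinical choice of modality. Section 4.3.5 already lists type of evaluation and percent stenosis among the data collected, and Appendix H lists one renal artery evaluation form. A breakdown by modality therefore looks feasible, although the form's content is under separate cover.

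**Downside.** The any-modality line includes duplex false positives, 4.5% to 10.8% shown against a true 2.0% in illustration D. That is why the CT/MR lines must stand beside it. With no added imaging, the CT/MR-confirmed line may rest on few subjects.

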#### **4.3.5 Baseline Renal Artery Anatomy Evaluation**

Adequate renal artery imaging is recommended to occur within 90 days prior to enrollment. Renal artery imaging by Duplex Ultrasound (U/S) should be performed to evaluate the subject's renal artery anatomy. Study investigators may consider requesting a computed axial tomography scan (CT scan) or utilize the procedural angiogram if the Duplex Ultrasound is inconclusive or shows any renal abnormalities.

Renal artery evaluation data collected will include but are not limited to:

- Type of evaluation - computed axial tomography (CT scan), duplex ultrasonography, angiography, Doppler, magnetic resonance (MR) angiography, or non-contrast MRI
- Length of artery(s)
- Diameter of artery(s)
- Number of main renal arteries
- Number of accessory renal arteries
- Presence and percent of stenosis
- Other abnormalities

---

SJM CONFIDENTIAL AND PROPRIETARY

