#### 4.5 Renal Denervation Procedure

The renal nerve ablation should be performed according to the EnligHTN™ Renal Denervation System Instructions for Use (IFU).

The renal denervation procedure should always be done with the aid of fluoroscopy. With the patient under local anesthesia, an introducer sheath will be inserted into the femoral artery using the standard percutaneous technique (modified Seldinger technique). A heparin bolus of 3000 to 5000 units will then be administered intravenously or per institution's standard of care. An 8 French guiding catheter sheath will be inserted to engage each main renal artery sequentially with the angiograms recorded. Images of the left and right main renal arteries will be recorded using the non-ionic contrast and the diameter and length of each of the main renal arteries will be measured.

Prepare the patient for standard electrosurgery. Select an appropriate basket size of the Basket Renal Denervation Catheter (small size for patient with renal artery diameter between 4mm and 6mm and large size for patient with renal artery diameter between 5.5mm and 8mm) should be chosen. The Basket Renal Denervation Catheter will be inserted with the tip of the catheter positioned proximal to the bifurcation of one of the main renal arteries and the corresponding images will be recorded. The basket on the Renal Denervation Catheter will then be opened, while the impedance of each electrode on the basket will be monitored. To begin the ablation, the "START" button on the RF Generator will be pressed with the impedance, temperature and RF energy delivery monitored and recorded during the process. The investigator will decide the location(s) and number of ablation sites/lesions (4 to 8 ablation sites/lesions are recommended) in the main renal artery. When the ablation procedure is completed in this main renal artery, the basket on the Catheter will be withdrawn from the artery with the Basket Renal Denervation Catheter fully closed. Images of the renal artery using the non-ionic contrast will be recorded. Any signs of renal artery irregularities (vasospasm, stenosis or dissection) will be checked.

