The same renal artery ablation procedure will be repeated for the other main renal arteries. When the ablation procedure for the main renal arteries are also completed, the basket on the Renal Denervation Catheter will be withdrawn from the artery with the Basket Renal Denervation Catheter fully closed and the catheter will be visually inspected and flushed with heparinized saline. Finally, the sheath will be removed according to the center's standard of care.

Procedural data collected will include but is not limited to:

- EnligHTN™ Renal Denervation System device information
- Guiding catheter used – manufacture
- Number of arteries ablated
- Number of ablations performed
- Device settings
- Procedure time
- Ablation time
- Fluoroscopic time
- Volume of contrast media

---

SJM CONFIDENTIAL AND PROPRIETARY

© 2012 – St. Jude Medical Cardiovascular Division: All rights reserved. No portion of this work may be reproduced in whole or in part without the express written permission of St. Jude Medical Cardiovascular Division.

Clinical Investigational Plan: EnligHTN II

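### The follow-up renal artery endpoint counts new stenosis or aneurysm only at an undefined site of ablation, and no specified analysis after 30 days covers the rest of the treated artery

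*Combined protocol and SAP*

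**What the plan says.** Section 3.2 and the synopsis set the renovascular safety objective at 6 months, and again at 2 and 5 years, in these words: "Assessment of renovascular safety as measured by new renal artery stenosis or aneurysm at the site of ablation". Section 7.4.2.2 keeps that restriction and adds the threshold: "The new renal artery stenosis (>50%) and/or aneurysm at the site of ablation per Renal Artery Imaging (CT/MR) will be summarized". The optional Kaplan-Meier analysis carries the same limit: "time to the first new renal artery stenosis and/or aneurysm at the site of ablation, as appropriate".

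Section 4.5 leaves lesion placement open: "The investigator will decide the location(s) and number of ablation sites/lesions (4 to 8 ablation sites/lesions are recommended) in the main renal artery". Its list of procedural data, introduced by "Procedural data collected will include but is not limited to", includes the number of arteries ablated and "Number of ablations performed". No lesion position is named.

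The only list of renal artery imaging items is the baseline list in Section 4.3.5. It opens with "Renal artery evaluation data collected will include but are not limited to" and includes "Presence and percent of stenosis". Section 4.8.9 schedules follow-up imaging at 6, 24 and 60 months but lists no data items for it.

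**The concern.** The endpoint needs a judgement that the text gives no means of making consistently. To count a case, someone must decide, up to five years after the procedure, whether a stenosis lies where energy was delivered. The plan does not say how close is close enough, where the lesion positions are to be read from, or who decides.

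The restriction also leaves out part of the vessel that the procedure touches. Section 4.5 has an 8 French guiding sheath engage each main renal artery. Section 6.1 lists renal artery stenosis among the possible events associated with the procedure, with no limit to the ablation site. The safety statement at 6 months, 2 years and 5 years is therefore narrower than the risk that the plan itself describes. This matters because the stated purpose is to evaluate safety further, and this is the only renal artery endpoint planned after 30 days.

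**Working it through.** The plan states no event rate, precision target or test for this endpoint, and Section 7.2 rules out a formal power analysis. There is no figure to reproduce, so the check is mainly textual.

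**1. Is the term defined?** The synopsis, Section 3.2 and Section 7.4.2.2 all use it. None ties it to a segment, to a distance from a lesion or to the whole treated artery.

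**2. Does the text plan the data needed to apply it?**

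| Needed | What the text names | Where |
|---|---|---|
| Lesion position | Counts of arteries and ablations; list not exhaustive | Section 4.5 |
| Stenosis position | Presence and percent, at baseline only; list not exhaustive | Section 4.3.5 |
| Stenosis position at follow-up | No items listed | Section 4.8.9 |
| Rule matching stenosis to lesion | None | Section 7.4.2.2 |

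**3. Where would an off-site stenosis appear?** Take a new stenosis above 50% in a treated artery, first seen on the 6-month image and away from any lesion.

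- Section 7.4.2.1 covers events within 30 days, so it does not apply.
- Section 7.4.2.2 excludes the case by location.
- Section 7.4.3 permits ad hoc and per-artery analyses but commits to none.
- Section 5.7.8 requires reporting of all serious events and all adverse device effects, and Section 12.3.2 has the Clinical Event Committee adjudicate these. Section 7.4 specifies no summary of them after 30 days. A silent, non-serious stenosis enters this route only if it is judged device related. The definition of procedure related in Section 5.7.8 is tied to events occurring during the procedure, which fits a late finding poorly.

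**4. Which way can the error run?** Two comparisons must be kept apart.

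- Against all new stenoses in treated arteries, a correctly applied at-site count is a subset and cannot be larger.
- Against the true at-site count, reported = true at-site − at-site cases called off-site + off-site or natural cases called at-site. This can be too low or too high.

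**5. Illustration of size.** Inputs: N = 500, the planned Primary Analysis population (Section 7.3), with every subject assumed imaged. The share p with a new stenosis above 50% or an aneurysm anywhere in a treated artery, and the fraction f of those lying off-site, are pure assumptions.

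Expected counted = N × p × (1 − f). Expected uncounted = N × p × f.

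| p | f | All in treated arteries | Counted | Rate reported | Uncounted |
|---|---|---|---|---|---|
| 2% | 25% | 10 | 7.5 | 1.5% | 2.5 |
| 2% | 50% | 10 | 5 | 1.0% | 5 |
| 4% | 25% | 20 | 15 | 3.0% | 5 |
| 4% | 50% | 20 | 10 | 2.0% | 10 |

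At a lower pair of assumptions, p = 1% and f = 10%, the uncounted expectation is 500 × 0.01 × 0.10 = 0.5 subjects. The chance of at least one uncounted subject is then 1 − (1 − 0.001)^500 = 0.39.

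**The case against.** Several points on the other side stand.

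- **Location may be recorded.** A reader might infer that location is not collected, or that the restriction cannot be checked. The documents do not support that. Both data lists are open-ended, the presence-and-percent item belongs to the baseline evaluation (when no ablation site exists yet), and Appendix H says the form contents are supplied separately. Section 4.5 also requires recorded angiograms, recorded catheter-position images and recorded post-ablation images. What can be said is that the text names no location item and no matching rule.
- **The bias is not one-sided.** A reader might infer that the restriction can only lower the reported rate. That holds only against the whole-artery count. Against the endpoint as defined, misattribution can go either way.
- **The restriction has a rationale.** The study has no control arm, runs for five years, and excludes baseline stenosis only above 30%. Limiting the count to the treated site helps to separate device effect from natural disease. This is a good reason to keep the at-site rate, and it makes replacing it as the headline debatable. It is no reason to omit the broader rate.
- **There are other capture routes.** Acute irregularities are checked after ablation without a site limit, events to 30 days are summarised, and serious events and device effects are reported and adjudicated. This narrows the gap to later findings, for which reporting is possible but no analysis is specified.

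If the sponsor meant the whole treated artery, the undercount disappears, but the text does not say so.

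**Conclusion.** The concern holds in a limited form. As written, the plan counts follow-up stenosis and aneurysm at an undefined location, names no data item or rule for deciding that location, and specifies no analysis after 30 days for a new finding elsewhere in a treated artery. Such a finding may still be reported as a serious adverse event or adverse device effect.

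The size is unknown. The figure of 2.5 to 10 uncounted subjects in 500 rests wholly on the assumed 2-4% and 25-50% and on complete imaging, and it is not evidence of an actual undercount. The endpoint is secondary and descriptive, so no test or sample size is affected. The point is worth acting on because the remedy is cheap and yields a safety rate that does not depend on the attribution judgement.

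**What to change.** In Section 7.4.2.2:

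1. Keep the at-site summary.
2. Beside it, at 6 months, 2 years and 5 years, report the percentage of subjects with any new stenosis above 50% or aneurysm in any treated renal artery, on the same denominator, with at-site cases shown as a subset.
3. State what counts as the site of ablation. If the separately supplied forms or the recorded images already hold lesion and stenosis location, say that the decision is made from them.

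The cost is a few sentences and one more table row, from imaging already scheduled. The objectives can stay as they are because the at-site measure is retained. The downside is that the broader rate will include some natural disease and may look slightly less favourable; the subset row lets a reader see the difference.
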